In this approach, `timevariable` represents the time until the event in question (e.g., recovery), `censorvariable` represents the censoring variable (e.g., 0= event observed, 1= event did not occur at the time of withdrawal, discharge, lost-to-followup, etc), and `treatmentvariable` represents the intervention (e.g., 0= remdesivir + placebo, 1= remdesivir + new treatment).

To perform a Cox proportional hazards analysis and generate the treatment hazard ratio along with its Wald confidence interval and p-value from the score test after adjusting for other covariates, the following SAS pseudocode will be used.

```
proc phreg data=dataset;
  class treatmentvariable(ref=placebolabel) othercovariates;
  model timevariable * censorvariable(1) = treatmentvariable othercovariates /
  ties=efron;
  hazardratio treatmentvariable / diff=ref cl=wald;
```

```
ods output hazardratios = hrest globaltest=pvalue;
run;
```

To assess the assumption of proportional hazards for Cox models, Kaplan-Meier curves for each treatment arm will be produced (PH assumption supported if curves do not cross). Restricted mean survival time along with its 95% CI will be reported to assess whether the results change if the PH assumption is not satisfied.

Proportional Odds analysis without MI:

The following SAS pseudocode will be used to perform the proportional odds analysis with treatment, baseline ordinal score and baseline steroid use as covariates to generate the treatment odds ratio, p-value, and predicted probabilities of the ordinal scale levels by treatment and ordinal score using complete data

```
proc logistic data=dataset out=imp_parms plots(only)=effect(x= ordscore_d8
  sliceby =baseordscorevar*trtvar individual connect);
  class baseordscorevar (param=ref ref=5) basesteroidusevar (param=ref ref=no
steroid use) trtvar (param=ref ref=placebolabel);
  model ordscore_d8 = trtvar baseordscorevar basesteroidusevar;
  oddsratio trtvar;
  ods output oddsratioswald = orest;
run;
```

For the endpoints analyzed by proportional odds, odds ratios between the binary progression strata will be computed, to support data understanding. For example, odds ratio, confidence intervals from logistic regression will be reported for treatment effect for the binary endpoint of OS= 1-7 vs 8, then OS= 1-6 vs 7-8, etc. Similar odds ratios across these 7 2x2 tables will support the proportional odds assumption.

95% Blaker confidence intervals for proportions/percentages:

```
proc freq;

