6.4.2. Covariates for Secondary Endpoints

The main analysis for time to sustained recovery will use baseline steroid use and actual baseline ordinal score as covariates in a Cox regression model. P-value from the score test of this adjusted Cox model will be used to compare the covariate adjusted time to sustained recovery between treatment arms. This analysis will be referred to as the primary analysis of the time to sustained recovery endpoint. In the supplemental analysis, time to sustained recovery endpoint will be analyzed using baseline steroid use, actual baseline ordinal score, continuous age, and continuous duration of symptoms prior to enrollment as covariates in the Cox model.

Survival without respiratory failure up to and including Study Day 29 will be analyzed only for subjects with an actual baseline ordinal score of 5 or 6. The main analysis for this endpoint will use a logistic regression model adjusted for baseline ordinal score (5 vs 6/7), baseline dexamethasone use (yes or no), continuous

baseline CRP value, and continuous age as covariates. Additionally, the proportion of subjects who are alive and without respiratory failure up to and including Study Day 29 will be presented by treatment along with 95% and 80% CI estimated from Kaplan Meier. As a sensitivity analysis, survival without respiratory failure will be analyzed using a logistic regression model adjusting for baseline steroid use and actual baseline ordinal score as covariates. A supplemental analysis of this endpoint will use a logistic regression model adjusting for baseline steroid use, actual baseline ordinal, continuous age, and continuous duration of symptoms prior to enrollment.

The analysis of the time to mechanical ventilation or death will include baseline ordinal score (5 vs 6/7), baseline dexamethasone use (yes or no), baseline CRP value and age as covariates in the Cox regression model.

A detailed list of covariates and subgroup analyses to be performed for secondary endpoints is also provided in [Table 6](#).

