6.8. Multiple Comparisons/Multiplicity

Analyses related to primary and key secondary endpoints will be conducted without adjustment for multiple endpoints and multiple arms. That is, all planned analyses will be conducted without statistical adjustment for multiplicity, with the main focus on the primary and secondary endpoints for each intervention versus placebo comparison.

However, a possible set of supplementary analyses described in the remainder of this section adjusting for multiplicity might be performed, but only if their inclusion appears likely to be helpful in interpreting the primary and secondary analyses results.

For this approach, adjusted p-values for multiple endpoints (primary and secondary continuous and binary endpoints) will be computed using the Westfall-Young permutation approach (specifically, the free step-down resampling method procedure that produces adjusted p-values that preserves the order of the endpoints for the unadjusted p-values) and results will be reported in [Table 44](#). Two analyses will be performed both based on complete data, one treating Day 8 ordinal score as a continuous variable and the other excluding Day 8 endpoint from the Westfall-Young analysis. Time-to-event endpoints will be excluded from both models.

A third analysis will provide adjusted P-values using Hochberg method. This analysis will include p-values from endpoints and will use p-value from multiple imputation where applicable. Results will be reported in [Table 45](#).

An additional global analysis will calculate Z-scores for all primary and secondary efficacy endpoints applicable to all subjects in the analysis population [3] and a global p-value will be calculated from the permutation test using z-scores from the linear model for continuous endpoints, cox model for time-to-event data, logistic regression for binary, and ordinal logistic regression model for continuous. For the logistic and log-rank test, the z-score can be calculated as the square root of the chi-square statistic of the treatment group variable from the adjusted model. A global test statistic vector will be constructed where each element is a Z score calculated from an endpoint in [Table 9](#).

The mean of the z-scores for all the endpoints will be calculated. A global p-value can then be obtained through a permutation test. Results of this global test will be reported in [Table 45](#).

Table 9: Endpoints to be included in the global analysis

Endpoint type	Endpoint

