Primary	Ordinal score at Study Day 8
Key Secondary	Time (days) to sustained recovery
Key Secondary	Sustained survival without respiratory failure (binary: 1=Yes or 0=No)
Secondary	Time (days) to at least 1 units improvement from baseline/Time (days) to at least 2 units improvement from baseline
Secondary	Difference from baseline ordinal score at Days 3, 5, 8, 11, 15, 22, 29
Secondary	Number of days ordinal score > 4
Secondary	Number of days ordinal score > 5
Secondary	Number of days ordinal score > 6
Secondary	Number of days of hospitalization
Secondary	Value of CRP, ferritin, D-dimer, LDH, fibrinogen
Secondary (safety)	14-Day mortality, 28-Day mortality, 59-Day mortality (binary: 1=Yes or 0=No)
Secondary (safety)	Time (days) to death

Pseudocode:

Method 1: Obtain Adjusted P-values from Westfall-Young for Continuous and Binary Endpoints using observed data

```
proc multtest data=dataset perm stepboot n=100000 seed=1234;
  class trt;
  test mean (C1 C2 C3/uppertailed) ;
      test mean (C4 C5 ... Cx/lowertailed) ;
  test fisher(B1 B2 B3 B4/lowertailed);
  test fisher(B5 B6 ... Bx/uppertailed);
  contrast 'Trt vs Placebo' -1 1;
  ods output pValues=pvals;
run;
```

Where C1 C2 ... Cx is a list of all continuous covariates and C1 C2 ... Cx is the list of all binary covariates. The contrast should be updated as needed so that the placebo group is the reference. Note that the variables are grouped depending on the direction of the hypothesis test.

Method 2: Obtain Adjusted P-values using Hochberg method: Use raw p-values as input from the primary analysis for all the endpoints in [Table 9](#).

```
proc multtest data=rawpvalues hoc out=adj_pvals;
run;
```

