If a subject's last assessment is before Day 57 and is discharged to a location other than hospice, another hospital, or long-term care facilities, the subject will be considered recovered at the time of discharge for the sensitivity analysis but may be reviewed by the Endpoint Review Committee, if other data suggests the subject may not be recovered (e.g., to a location other than a private residence or discharged on high flow oxygen). If a subject is discharged to hospice or another hospital, or is a special case where recovery handling may be unclear, the subject's data may be reviewed by the Endpoint Review Committee to make the determination of whether the subject should be considered to have sustained recovery and, if so, at what time point in the analyses. Subject data to be reviewed as part of this determination will include the reported clinical status scores while hospitalized, where the subject was discharged to (e.g., private residence, rehabilitation facility, long-term care/nursing home, comfort care), and any information regarding readmittance. Additional information may be solicited to assess recovery.

Refer to [Table 6](#) for a list of covariates and subgroup analyses for this endpoint. Refer to [Table 7](#) for imputation methods to be applied to this endpoint.

The main analysis of the first key secondary endpoint (time to sustained recovery up to and including Study Day 60) conducts a score test to compare treatment to control up to and including Study Day 60. The treatment median survival time, confidence intervals and p-value from the score test will be presented ([Table 28](#)). Restricted mean recovery time estimates will be provided for each treatment group and actual baseline ordinal score stratum as well as the difference in restricted mean recovery time between treatment groups within each of the baseline ordinal score strata ([Table 29](#)).

Kaplan-Meier curves for each treatment arm will be presented and supplemented with the hazard ratio estimate, p-value, and the number of subjects at risk in each treatment at Study Day (not necessarily actual Study Days 1, 3, 5, 8, 11, 15, 22, 29, and 60) ([Figure 8](#)).

If the key secondary endpoint is different than what is covered in this SAP, it will be highlighted for each individual stage in the corresponding stage-specific appendix along with the subsequent analysis.

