The time to mechanical ventilation or death up to and including Day 29 will be defined as the elapsed time (in days) from Study Day 1 to date of mechanical ventilation or death. Any subjects whose last assessment is prior to obtaining the event and prior to Day 26 (beginning of Day 29 window) will be censored at the date of their last observed assessment. For the sensitivity analysis of this endpoint, subjects whose last assessment is

prior to obtaining the event and who were discharged to a location other than LTAC, hospice care, or other hospital will be considered recovered and censored at Day 29. For both primary and sensitivity analysis of this endpoint, subjects who complete follow-up will be censored Day 29. Events that occur after Day 29 will be censored at Day 29. A table will present median time to event along with corresponding 95% and 80% confidence intervals for each treatment along with the hazard ratio estimate and score test p-value from a Cox-proportional hazard model (Table 42). The Cox model will include as covariates baseline ordinal score, baseline CRP value, continuous age, and baseline dexamethasone use. Differences in time-to-event endpoints by treatment will be summarized with Kaplan-Meier curves (Figure 11). Analyses will be performed on the mITT population for those subjects who at baseline have an ordinal score of 5 or 6, CRP<150 mg/L, and age<85 years and results will be reported in Table 42. This analysis will be repeated for all subjects in the mITT population and results will be reported in Table 43.

Refer to Table 6 for a list of covariates and subgroup analyses for this endpoint. Refer to Table 7 for imputation methods to be applied to this endpoint.

Hospitalization

Duration (in days) of hospitalization will be defined as the number of days subject is hospitalized for COVID-19-related reasons starting from the date of randomization. It will be calculated as the total number of days hospitalized, including readmissions for COVID-19-related reasons. It will also be calculated as the total number of days hospitalized, including any readmissions regardless of cause. See Section 6.5 for the plan for handling subjects who do not have data through Day 29 or die prior to Day 29.

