Female	Treatment A (N=X)	x	x.x	x.x	x.x, x.x	x.x, x.x	x.x	x.x, x.x	0.xxx
	Treatment B (N=X)	x	x.x	x.x	x.x, x.x	x.x, x.x			
	P-value for interaction ^e								0.xxx
CI=Confidence Intervals. N=Number of subjects in modified intent-to-treat (mITT) population. n= Number of unique recovered subjects that satisfies the row criteria. ^a Hazard Ratio (HR) is the hazard ratio calculated from the Cox Proportional Hazard Model comparing Active treatment vs Placebo. All subjects lost to follow-up before recovery are censored at last assessment date. ^b Primary with Sensitivity Imputation 1: Subjects discharged to a location other than LTAC, hospice care, or other hospital are considered recovered at Day 60. The rest of lost to follow-up subjects are censored at last assessment date. Model ^a was fit to estimate the HR, 95% CI and p-values. ^c Supplemental Analysis 1 (age and duration of symptoms prior to enrollment): In addition to the variable included in the model described in ^a , age and duration of symptoms prior to enrollment as additional covariates were added to the model when estimating the HR, 95% CI and p-values. Same censoring as in model ^a . ^d For the subgroup analyses, the model described in ^a was performed for each level of the subgroup. ^e P-value is based on the Cox adjusted model or P-value from interaction Type III test in subgroup analysis where the interaction between subgroup and treatment is being added to the Cox Proportional Hazard Model.									

Table 29: Time to Sustained Recovery through Day 60 by Treatment Group, Actual Baseline Ordinal Score, and Analysis Population: Restricted Mean Survival Time Analysis

Analysis Population	Treatment Group	Actual Baseline Ordinal Score	n	Tau ^a	Restricted Mean Recovery Time (Days)			Difference		
					Estimate	95% CI	80% CI	Estimate	95% CI	80% CI
mITT	Treatment A (N=X)	5	x	x	x.x	x.x, x.x	x.x, x.x	x.xx	x.xx, x.xx	x.xx, x.xx
	Treatment B (N=X)		x	x	x.x	x.x, x.x	x.x, x.x			
	Treatment A (N=X)	6	x	x	x.x	x.x, x.x	x.x, x.x	x.xx	x.xx, x.xx	x.xx, x.xx
	Treatment B (N=X)		x	x	x.x	x.x, x.x	x.x, x.x			
	Treatment A (N=X)	7	x	x	x.x	x.x, x.x	x.x, x.x	x.xx	x.xx, x.xx	x.xx, x.xx
	Treatment B (N=X)		x	x	x.x	x.x, x.x	x.x, x.x			
	Treatment A (N=X)	Any BOS	x	x	x.x	x.x, x.x	x.x, x.x	x.xx	x.xx, x.xx	x.xx, x.xx
	Treatment B (N=X)		x	x	x.x	x.x, x.x	x.x, x.x			
ITT	Treatment A (N=X)	5	x	x	x.x	x.x, x.x	x.x, x.x	x.xx	x.xx, x.xx	x.xx, x.xx
	Treatment B (N=X)		x	x	x.x	x.x, x.x	x.x, x.x			

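### The only p-value the Cox pseudocode saves is a joint test of treatment and covariates, not the adjusted treatment test the SAP text asks for

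*SAP*

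**What the plan says.** SAP section 6.1 introduces the Cox code as the way to "generate the treatment hazard ratio along with its Wald confidence interval and p-value from the score test after adjusting for other covariates". The MODEL statement then lists `treatmentvariable othercovariates`, and the only results saved are the hazard-ratio table and the global test: "ods output hazardratios = hrest globaltest=pvalue".

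The text elsewhere describes a treatment comparison. Section 6.4.2, on sustained recovery: "P-value from the score test of this adjusted Cox model will be used to compare the covariate adjusted time to sustained recovery between treatment arms". Section 8.2.1 says the main analysis "conducts a score test to compare treatment to control up to and including Study Day 60". Section 8.2.2, on ventilation or death, asks for the "hazard ratio estimate and score test p-value from a Cox-proportional hazard model".

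The table footnotes do not name the tested term. Table 28, for example, says "P-value is based on the Cox adjusted model or P-value from interaction Type III test in subgroup analysis". Tables 32, 42 and 54 likewise refer only to the Cox model or its score test.

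**The concern.** The global score test and the treatment score test are the same only when treatment is the sole term in the model. With covariates present, the global null says that treatment has no effect and that no covariate predicts the outcome. For sustained recovery this is a 3-df test (treatment, baseline ordinal score, steroid use). For ventilation or death it is a 5-df test (treatment, baseline score, dexamethasone, CRP, age).

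Two errors follow if the code is used as printed. If a covariate is prognostic, the p-value is too small whatever the drug does. If none is, the extra degrees of freedom cost power. The hazard ratio and Wald interval come from a separate and correct statement, so the p-value and interval in one table row can disagree.

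The affected analyses are time to sustained recovery and its within-subgroup p-values, 1- and 2-point improvement, ventilation or death, and the adjusted mortality models. The optional Hochberg adjustment in section 6.8 takes in the same values ("Use raw p-values as input from the primary analysis for all the endpoints in" Table 9). In rows restricted to one baseline score, that covariate drops out and only the remaining ones contaminate the test.

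**Working it through.** **No figure to reproduce.** The SAP states no size or power for any Cox test, so the check asks how often each test rejects when the drug has no effect.

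**Inputs from the documents.** 100 per arm (SAP section 5); two binary covariates for sustained recovery (section 6.4.2); significance at 0.05 (section 6.1); deaths before recovery kept at risk to Day 60 (Table 7); a 10-day recovery time on remdesivir (protocol section 2.2.2).

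**Assumptions not in the documents.** Share at baseline score 6/7 of 50% or 30%; recovery hazard ratio (HR) for 6/7 against 5 varied from 1.0 down to 0.33; 80% on steroids, with no prognostic effect; the recovery plateau and number of recoveries.

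**Analytic check.** With true treatment HR 1, the global statistic is approximately noncentral chi-square on 3 df, with noncentrality D × q(1−q) × ln(HR)². Here D is the number of recoveries, q the share at 6/7 and HR the prognostic ratio. For D = 150 and q = 0.5:

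- HR 0.8: 150 × 0.25 × 0.0498 = 1.87; rejection 18%
- HR 0.67: 150 × 0.25 × 0.160 = 6.0; rejection 52%
- HR 0.5: 150 × 0.25 × 0.480 = 18.0; rejection 96%

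Over D = 120 to 170 and q = 0.3 to 0.5, the ranges are 13–20%, 36–58% and 84–98%.

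**Simulation 1** (2,000 trials per setting, Efron ties, whole-day times). The cumulative recovery hazard is 1.8 × (1 − exp(−0.0486 × day)). At Day 10 this is 0.693, so half have recovered. At Day 60 it is about 1.70, so about 82% have recovered. Baseline score was centred, which keeps recoveries at about 161–164. True treatment HR is 1.

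| Prognostic HR, 6/7 vs 5 | 1.0 | 0.8 | 0.7 | 0.6 | 0.5 |
|---|---|---|---|---|---|
| Global p<0.05, half at 6/7 | 5% | 21% | 46% | 80% | 97% |
| Global p<0.05, 30% at 6/7 | 5% | 16% | 38% | 67% | 91% |
| Global p<0.05 but 95% CI includes 1, half at 6/7 | 3% | 18% | 42% | 76% | 91% |

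The 1-df treatment score test rejected in 5–6% of trials throughout.

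**Simulation 2** (2,000 trials per setting, half at 6/7). Recovery times are exponential, and 10% of subjects never recover whatever their baseline score, which weakens the hazard ratio the Cox model sees. There were 150–175 recoveries.

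| Prognostic HR, 6/7 vs 5 | 1.0 | 0.8 | 0.67 | 0.5 | 0.33 |
|---|---|---|---|---|---|
| Global p<0.05 | 5.9% | 12.4% | 31.9% | 80.0% | 99.8% |
| Treatment score test p<0.05 | 4.8% | 4.8% | 5.1% | 5.5% | 6.5% |

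**Loss of power.** With true treatment HR 1.5, D = 150 and non-prognostic covariates, the noncentrality is 150 × 0.25 × ln(1.5)² = 6.2. Power is 70% on 1 df and 53% on 3 df. Simulation 1 gives 73% against 57%; in 19% of those trials the interval excludes 1 while the global p-value is 0.05 or more. Simulation 2 gives 38% against 26%.

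**The case against.** The strongest reply is that the block is labelled pseudocode and the text leaves no doubt about intent. A joint test of treatment and covariates is not adjusted for those covariates, and sections 6.4.2 and 8.2.1 name the arms being compared. The templates also need completing anyway: the Cox block sets no 80% level, and the risk-difference code in section 6.1 merges `predp` with itself. A competent programmer may correct the output line, and a p-value that contradicts its own interval would draw attention. The intended test is indeed clear, so this is a wrong output line rather than an undecided hypothesis. But section 6.1 says the code will be used, it is the only stated source of the Cox p-value, and no rule in the SAP puts text above code. A mismatch found after unblinding would mean choosing between two p-values, each with SAP support.

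The size is also open to challenge, and that point stands in part. If the 10-day median belongs to score 5 rather than the average subject, recoveries at prognostic HR 0.5 fall to 139. With fewer recoveries, global rejection is about 11–13% at HR 0.8 and 73–85% at HR 0.5. A range is therefore the honest summary.

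One supporting passage should not be pressed too far. Section 6.8 says "the z-score can be calculated as the square root of the chi-square statistic of the treatment group variable from the adjusted model", but that sentence concerns z-scores for the logistic and log-rank tests in an optional analysis. The Hochberg table is optional too.

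**Conclusion.** The concern holds. As printed, the code returns a p-value for a different hypothesis from the one stated, and it does so for a key secondary endpoint. Across the scenarios tried, with no drug effect, rejection at 0.05 is roughly 11% to 21% for a prognostic HR of 0.8 and 73% to 98% for 0.5, against a nominal 5%. With no prognostic covariate, size is kept at about 5–6% but power falls. Exact sizes depend on assumed prognostic strength, severity mix and number of recoveries. A null effect of baseline score is an unlikely assumption, because the SAP both stratifies on it and adjusts for it.

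Not affected are the Day 8 proportional-odds analysis (its code in section 6.5.2 keeps only the treatment row), the interim and promising rules, all hazard ratios and Wald intervals, and the improvement figures, which carry log-rank p-values. This should be fixed before analysis, but it does not threaten the primary conclusion.

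**What to change.** In section 6.1, replace the global-test output with the 1-df score test of the treatment term: add `type3(score)` to the MODEL options and save the treatment row of the Type 3 table, or specify a nested-model score comparison. State that the p-value is the adjusted score test of the treatment term in sections 6.4.2, 8.2.1 and 8.2.2 and in the footnotes to Tables 28, 32, 33, 42, 43 and 54.

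For two endpoints, first settle whether the model is adjusted at all. Table 6 specifies no covariate adjustment for time to death by Day 29 and for the safety composite. Section 9.4 and the Table 54 footnote (death) and the Table 56 footnote (composite) say the model adjusts for baseline ordinal score and steroid use. If unadjusted, the global test already is the treatment test there.

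The cost is one line of code and a few words of text. No new data are needed.
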